### 2.9.3 Analysis of colorectal cancer occurrence after endoscopic examination

The analyses above will be complemented by analyses of subsequent clinical CRCs in the follow-up period where available. Such events are rare and estimates will therefore be imprecise, but the analysis will add some value to the exercise, by enabling us to assess the trade-off between harvest of polyps at subsequent examination and expected number of cancers occurring before the subsequent examination. Again the analysis will proceed in steps of increasing complexity, beginning with simple description of rates of cancers by time since and findings at last examination, through regression modelling to formal multistate models.

We will assess the absolute risk of CRC using Kaplan-Meier curves and will compare the incidence of CRC to that expected in the general population, both in the absence and in the presence of surveillance. We will use Cox proportional hazards models to assess the effect of surveillance on the risk of CRC, with the number of follow-up visits included as a time-varying covariate.

The models will also be used to assess the relationship between patient, polyp and procedural characteristics at baseline and CRC risk. We will use univariable models to estimate unadjusted hazard ratios and will use multivariable models to estimate the effect of surveillance adjusted for patient, polyp and procedural characteristics and to identify independent predictors of future CRC risk. The risk factors identified in the multivariable models will then be used to aid in the creation of distinct subgroups. These subgroups will then be scrutinised to determine whether in any subgroup the CRC risk after baseline is low enough relative to the general population to not warrant surveillance. Conversely, in subgroups that do appear to benefit from surveillance, the results will be examined to see whether the risk of CRC becomes low enough after a certain number of exams in order for surveillance to safely cease.

In order to examine appropriate surveillance interval lengths, we will analyse the yield of advanced adenomas and CRC at surveillance visits by interval in patients who attended follow-up after baseline. In the high-risk group we will also examine the effect of a short vs a longer surveillance interval (one year as recommended vs longer than one year) on long-term CRC incidence. In order to investigate this, we will create crude groupings based on the interval to first follow-up exam and the incidence of CRC between groups will be compared.

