# 2.3.1 Analysis of risk of cancer or advanced adenomas with varying frequency of colonoscopy surveillance

The aim of the statistical analysis is to answer the following questions:

- 1. Is there substantial heterogeneity of results at subsequent examination in terms of detection rates of advanced adenomas or CRC according to baseline characteristics and interval to first follow-up colonoscopy?
- 2. If so, is there a subgroup that does not need subsequent examination identifiable at baseline, and is the magnitude of this subgroup meaningful?
- 3. For those who do need follow-up can we identify a group for whom an interval of 3 years is too long? Similarly is there a group for whom 3 years is too short?
- 4. For the latter group, how long can the interval safely be extended to?
- 5. Is there a subgroup who needs a second examination but no further follow-up thereafter, and if so, how is the group identified from the baseline and first follow-up examination results?
- 6. What is the risk of CRC in each adenoma risk-group defined according to current UKadenoma surveillance guidelines:
  - a) What is the long-term CRC risk in those who have no surveillance?
  - b) What is the long-term CRC risk in those who do have at least one, or two or more surveillance exam(s)?
  - c) Are there sub-groups in which CRC risk is low enough not to warrant surveillance?
  - d) Among those whose risk is determined high enough to require surveillance, when would CRC risk become sufficiently low to safely stop surveillance?
- 7. Should risk-groups be redefined based on long-term CRC risk such that some patients might be reclassified as lower risk?
- 8. What are appropriate surveillance intervals within defined risk groups to warrant colonoscopy but not result in unacceptably high interval cancers?

9. What are the health and economic impacts of refined risk groups and surveillance intervals?

For questions 1-4 the analysis will draw on data on the baseline examination and the first follow-up examination, in particular how the findings at the latter relate to those at the former. For question 5, we will relate the findings at second and subsequent follow-up examinations to those at baseline and first follow-up examination.

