# 2.6.1 Informed consent

Fully informed consent to use the patient data in this study will not be possible, due to its retrospective nature, although many programmes obtain consent from subjects for use of their results for audit and improvement of the service. For much of the analyses it will be possible to anonymise the data, but where the study researchers will have to match data from different databases to provide adequate information for the statistical analysis anonymisation will not be possible. Such matching will be carried out prior to the statistical analysis and the data reanonymised so that those charged with the analysis do not have identified data. Identified data will need to be supplied to ONS if the cohort is to be followed using the national cancer registries as we would like to do.

We will amend our Patient Information Advisory Group (PIAG) section 60 approval, now section 251 approval, to request permission to collect additional data to the end of 2016 where available and include the analysis of the data to include the low- and high-risk adenoma groups.

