#### Protocol sample size table, section 2.8.2 - updated

The hospital dataset is comprised of endoscopy / pathology data originating in the participating hospitals, colorectal cancer incidence data from NHS Digital, ONS mortality data (via NHS Digital), National Records of Scotland mortality data and cancer registration data from NHS National Services Scotland. This is the dataset that we will be using to conduct the All Adenomas study; the 'All Adenomas study database'.

Of the six additional screening datasets listed in section 2.8.1 of the protocol, several datasets were excluded for reasons such as data security, permission denied, insufficient data and data not being electronically linked (so that manual data collection would be too costly and lengthy to obtain). Three datasets remained: The UK Flexible Sigmoidoscopy Screening Trial, the English data from the UK National Pilot of FOBT screening and the Kaiser Permanente dataset. These three datasets have been combined to make an independent 'screening dataset' which is not linked to the All Adenomas study database. The screening dataset will be used to validate the findings in the All Adenomas study database.

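### Surveillance exams are seen only in participating hospitals' files while cancers come from national registers, and the plan neither ends follow-up when exam data end nor tests for unseen exams

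*Combined protocol and SAP*

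**What the plan says.** **Exposure.** Section 2.9.3 assesses surveillance by Cox regression, "with the number of follow-up visits included as a time-varying covariate". It also compares CRC incidence with general-population expectation, without and with surveillance. Subgroups whose risk is low enough on that comparison may be judged not to need surveillance. Question 6a in section 2.3.1 asks: "What is the long-term CRC risk in those who have no surveillance".

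**Data sources.** Appendix 1.0, part a, states: "The hospital dataset is comprised of endoscopy / pathology data originating in the participating hospitals, colorectal cancer incidence data from NHS Digital". It adds national mortality data and, for Scotland, "cancer registration data from NHS National Services Scotland". It then says: "This is the dataset that we will be using to conduct the All Adenomas study".

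**Dates.** The updated sample size table in Appendix 1.0 describes the intermediate-risk cohort with data to the end of 2014. Section 2.6.1 plans "to request permission to collect additional data to the end of 2016 where available". The documents give no end date by hospital or by type of data.

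**What is absent.** Sections 2.3.1 and 2.9 and Appendix 1.0 contain no last date of complete exam data, no censoring at such a date, no second source of exams and no sensitivity analysis for exams done outside the participating hospitals.

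**The concern.** Exposure and outcome have different catchments. A cancer registered nationally is counted wherever the patient was treated. A colonoscopy is counted only if it took place at a participating hospital, within the period covered by that hospital's files. A patient examined elsewhere, or after the files stop, keeps the old visit count and still contributes person-time and possibly a cancer.

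The decisions at stake are those in questions 6a, 6c and 6d: the risk without surveillance, which subgroups can do without it, and when it can stop. Each depends on the no-visit and low-visit groups being what their labels say. The interval comparisons under question 8 are touched too, because a missed exam lengthens the apparent interval.

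**Working it through.** The plan states no figure for exam completeness, so there is none to reproduce. The size has to be illustrated under assumptions.

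**Inputs from the documents** (Appendix 1.0, updated sample size table, intermediate-risk, to end 2014): 11,944 patients, of whom 7,046 had at least one recorded follow-up colonoscopy. None recorded: 11,944 − 7,046 = 4,898 (41%). The table gives no matching counts for the low- and high-risk groups.

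**Assumptions, not in the documents:** true hazard ratio (HR) 0.6; 10 years of follow-up for everyone; first exam at year 3; a share q of truly surveilled patients has no recorded exam, with q = 5%, 10% or 20%.

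**Step 1, hidden patients.** h = 7,046/(1 − q) − 7,046 = 371, 783 or 1,762.

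**Step 2, recorded no-visit person-time.** The covariate is time-varying, so time before a recorded exam belongs here too: 7,046 × 3 + 4,898 × 10 = 21,138 + 48,980 = 70,118 years.

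**Step 3, misclassified share.** Each hidden patient is truly unsurveilled for 3 years and misclassified for 7, so m = 7h/70,118.

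**Step 4, effect.** Recorded/true no-surveillance rate = 1 − m(1 − HR). Recorded HR = HR/[1 − m(1 − HR)].

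| q | h | 7h | m | No-surveillance rate understated by | HR reads |
|---|---|---|---|---|---|
| 5% | 371 | 2,597 | 3.7% | 1.5% | 0.61 |
| 10% | 783 | 5,481 | 7.8% | 3.1% | 0.62 |
| 20% | 1,762 | 12,334 | 17.6% | 7.0% | 0.65 |

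With the first exam at 4.5 years, the denominator is 7,046 × 4.5 + 48,980 = 80,687 and the misclassified time is 5.5h. The understatement is then 1.0%, 2.1% or 4.8%, and the HR reads 0.61, 0.61 or 0.63.

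**Step 5, the general-population comparison.** A true ratio R is recorded as R × [1 − m(1 − HR)]. In the table's 10% case, a true ratio up to 1/0.969 = 1.03 would read as 1.00 or less; in the 20% case, up to 1/0.930 = 1.08. A true ratio of 1.20 would still read 1.20 × 0.930 = 1.12.

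**Step 6, does the direction always hold, and does censoring help?** I simulated 2 million patients over 10 years under assumed values: 60% have a first exam at a time between years 1 and 8, and the baseline CRC rate is 2 per 1,000 per year. Exam files end at year 4 for half the patients. True and recorded figures in a row come from the same simulated patients.

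| Scenario | No-surveillance rate per 1,000 per year, true / recorded | HR, true / recorded |
|---|---|---|
| HR 0.5, early-ending files only | 2.01 / 1.92 | 0.50 / 0.52 |
| Same, censored at end of exam files | 2.02 / 2.02 | 0.50 / 0.50 |
| HR 0.5, early-ending files and 20% of exams elsewhere | 2.01 / 1.86 | 0.51 / 0.55 |
| Same, censored at end of exam files | 2.01 / 1.94 | 0.50 / 0.52 |
| HR 0.7, early-ending files, 20% elsewhere in patients at twice the baseline risk | 2.17 / 2.17 | 0.76 / 0.63 |

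Censoring removes the bias from early-ending files but not from exams done elsewhere. In the last row the rate is unbiased and the HR moves away from 1. With a true HR of 1.0 the formula in step 4 gives no bias.

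**The case against.** **The date gap is not stated.** A reader might infer that exams stop before cancers at some hospitals. The documents do not say so. The availability qualifier in section 2.6.1 covers all the additional data, and the rationale in section 2.3 extends procedures, cancers and deaths together. The 2014 date describes the earlier intermediate-risk cohort. The plan is also silent on when follow-up ends; it does not say that follow-up outlasts the exam data. This stands. The difference in catchment is stated, however, and does not depend on dates.

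**The direction is conditional.** A reader might infer that the gap always favours the hypothesis in section 2.2.4 that less surveillance is enough. That needs surveillance to be protective and unseen exams not to cluster in higher-risk patients. The documents establish neither, and the last row of the simulation shows the HR moving the other way.

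**The size is easily overstated.** Treating surveillance as fixed and dividing hidden patients by 4,898 gives 8%, 16% or 36% misclassified and an understatement of 3%, 6% or 14%. The model is time-varying, so this ignores true unsurveilled time before each exam and roughly doubles the effect.

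**There are other checks.** Appendix 1.0 reserves an independent screening dataset for validation, and one of its trials offered surveillance under a set protocol. That is a partial external check, but the set is not linked and cannot supply missing exams. Internal cross-validation would carry the same misclassification into every split.

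**Conclusion.** The concern holds in a limited form. The plan observes exams and cancers over different catchments, and no rule stops an unseen exam from being analysed as no surveillance. The likely direction is towards understating no-surveillance risk, on the two conditions above; if they fail, the bias can vanish or reverse. Under the stated assumptions the understatement is about 1.5% to 7% with a first exam at year 3. That cannot hide a large excess over the general population. It can decide the outcome for a subgroup a few per cent above it, which is where a conclusion that surveillance is not warranted would be drawn. The true size is unknown, because the documents say nothing about exam completeness.

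**What to change.** In section 2.9.3:

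1. Add: *For analyses by surveillance (questions 6–8), follow-up is censored at the earlier of the end of cancer registration and the date to which the patient's hospital supplied complete endoscopy data.* Report that date for each hospital.

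2. Add a bias analysis for exams done elsewhere, since censoring does not reach them. Reassign a range of recorded no-surveillance person-time, for example 5%, 10% and 20%, to surveilled status. The reassigned time should carry the lower event rate implied by the surveillance HR: moving time and events in proportion would leave the no-surveillance rate unchanged. In the simple case, inverting step 4 gives corrected HR = HR_rec(1 − m)/(1 − m × HR_rec), where HR_rec is the recorded ratio, and the corrected no-surveillance rate is the recorded rate divided by 1 − m(1 − corrected HR). Include a case in which patients examined elsewhere have higher baseline risk. Report whether each conclusion that a subgroup does not warrant surveillance changes. The documents give no basis for a fixed pass threshold, so none should be set.

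The cost is one sentence, one date per hospital and a short analysis. Some late person-time and CRCs leave the surveillance comparisons, but they can stay in the overall description of risk.

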#### 2.2.4 Current UK recommendations

In 2000, [name] and [name] at St Mark's Hospital were invited to undertake a review of the literature and to develop guidelines for the colonoscopic surveillance following adenoma detection (see figure below). We identified a low-risk group for which it was suggested that colonoscopic surveillance might not be necessary and a high-risk group for which surveillance is definitely indicated, at least 3 yearly and maybe more frequently initially. This latter group includes people with 5 or more adenomas or 3-4 adenomas at least one of which is advanced; this group comprises only around 5% of people with adenomas. This left an intermediate risk group for which there is no evidence to indicate that it is safe not to offer surveillance. The available evidence suggested that it might be safe to stop surveillance after two negative exams, depending on the age of the patient and the quality of the examinations. However, it is possible that patients with intermediate adenomas are a heterogeneous group with respect to their risk of developing CRC and that longer intervals might suffice for a subgroup. It is also possible that it is not necessary to have two negative exam might be sufficient.

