The statistical analysis strategy will be split into three stages: (1) analysis of first follow-up findings in relation to baseline findings; (2) analysis of second and subsequent follow-up findings in relation to baseline and first follow-up findings, and (3) analysis of rates of symptomatic CRC in the years after final endoscopic examination.

Analyses will be performed both including and excluding those with first follow-up less than 3 years after baseline, as this may be a reflection of clinical opinion of extra high risk. Results of all analyses will be confirmed by internal cross-validation.

For questions 6 – 8 our statistical analyses will focus on the long-term CRC incidence after

baseline. To assess the effect of surveillance on CRC risk, we will compare the incidence of CRC both in the absence and presence of surveillance, and compare CRC risk with that expected in the general population. Cox proportional hazard models will be used to assess the relationship between baseline characteristics and CRC risk to identify subgroups in which CRC risk is low enough to justify less intensive surveillance and reclassification of risk. In those who benefit from surveillance, the CRC risk will be examined after multiple exams to estimate when surveillance could safely stop, or multiple intervals to estimate the appropriate interval length between surveillance exams.

Additional health economic analyses will be conducted to estimate the cost implications of alternative surveillance strategies (question 9).

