#### UK Hospital Endoscopy and Pathology databases

We shall obtain datasets from several UK hospital endoscopy units which routinely record the date and type of examination, indication for colonoscopy and diagnosis, and the size and location of any polyps detected. It will then be necessary to search the hospital pathology databases for records with the SNOMED codes for adenomas. The datasets so derived will then be matched to identify patients with intermediate adenomas who have undergone baseline and surveillance colonoscopies. Since this is a study of intermediate adenomas detected in average risk individuals who are likely to undergo population screening, patients with the dominantly inherited syndromes (FAP, HNPCC, etc) or inflammatory bowel disease will be excluded.

We have undertaken a preliminary investigation to determine how many people with intermediate adenomas can be obtained by searching databases in hospitals which have used an endoscopy database for at least 5 years. We performed a pilot study using the St Mark's Hospital endoscopy database, which has been operational since 1995, and identified around 900 patients with an intermediate adenoma and a baseline colonoscopy, and around 150 who have had at least one follow-up colonoscopy (this data needs more cleaning but is approximately correct). We have not yet completed our investigations but so far we estimate that we need to contact 20 hospitals to achieve the required sample size.

	Patients with intermediate adenomas (n)		
	Baseline	≥ 1 follow-up	≥ 2 follow-up
		colonoscopy	colonoscopies
Endpoint	Colorectal	Advanced	Advanced
	cancer	adenoma	adenoma
Total number of endpoints required	60	198	36
Total number of cases required	10,000	6,600	1,200
UK FS Screening trial*	1925	1453	484
St Mark's Adenoma Follow-up trial	603	359	124
Nottingham FOBT trial*	582	483	279
UK Pilot of FOBT screening*	1139	850 (by 2005)	0
Kaiser Permanente FS screening service*	2000+	1500+	500+
VA Colonoscopy screening study*	-	388	0
St Mark's hospital endoscopy database	900	250	100 (estimate)
20 other UK endoscopy databases	6,000	1,000	400 (estimate)
Total	11,149	4,787*	1287

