#### 2.9.2 Second and subsequent follow-up

Analysis of findings at second and subsequent follow-up will closely parallel those of first follow-up with the slight complication of the need to consider their joint association with both baseline and first follow-up results. As for part (a) of the analytic strategy, simple analysis of rates of polyps by time since last examination, the major difference will be stratification by the two previous examinations.

For part (b), the logistic regression, the endpoint (y-) variable will be the finding at second or subsequent follow-up and the x-variables studied will be firstly as before the time since last examination and baseline. Then we will augment the model with findings at first follow-up examination to see if these significantly improve prediction of findings at second and subsequent follow-up. The logistic regression model would now be

where  $x_1$  represents time since last examination,  $x_2$  size of polyp at last examination,  $x_3$  multiplicity of polyps at last examination,  $x_4$  presence of polyps at first follow-up examination etc.

The formal multistate modelling in (c) will be carried out to model sensitivity, incidence and

progression after the first follow-up. The results will give a further indication of the desirability or otherwise of subsequent follow-up beyond the first one and of changing the frequency of examination after the first follow-up.

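### The Cox model for the number of follow-up visits has no stated control for findings at earlier follow-up exams, so hazard ratios for second and later exams are open to time-varying confounding

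*Combined protocol and SAP*

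**What the plan says.** Section 2.9.3 states: "We will use Cox proportional hazards models to assess the effect of surveillance on the risk of CRC". The exposure enters as a running count that is updated during follow-up: the model is fitted "with the number of follow-up visits included as a time-varying covariate". The adjusted estimate comes from "multivariable models to estimate the effect of surveillance adjusted for patient, polyp and procedural characteristics". That sentence does not say when the characteristics are measured. The sentence opening the same paragraph does, describing "the relationship between patient, polyp and procedural characteristics at baseline and CRC risk". Section 2.3.1 agrees for questions 6 to 8: "Cox proportional hazard models will be used to assess the relationship between baseline characteristics and CRC risk".

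Findings at follow-up appear in two other places:
- Section 2.9.3 begins with a description of cancer rates by time since, and findings at, the last examination. It then mentions regression and multistate models in general terms.
- Section 2.9.2 uses them in the logistic regression for findings at second and later follow-up: "Then we will augment the model with findings at first follow-up examination to see if these significantly improve prediction".

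Neither section puts them into the Cox model for CRC, and no method for time-varying confounding is named. The one safeguard of this kind is in section 2.3.1, which repeats analyses with and without patients whose first follow-up came before 3 years. It concerns the timing of the first visit only.

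**The concern.** The exposure changes over time, but the stated confounders are fixed at baseline. A variable measured during follow-up confounds the effect of a further visit if it influences whether that visit happens and also predicts the outcome. The documents supply both links.

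- **Findings to visits.** Section 2.2.4 suggests that "it might be safe to stop surveillance after two negative exams", depending on age and exam quality. Where this is followed, patients who continue are enriched for positive exams.
- **Findings to CRC.** Section 2.2.2 reports a 3-fold risk with large, tubulovillous or villous adenomas, and 5-fold when they are also multiple. Section 2.8 gives about 4.5 per 1,000 per year in a high-risk subgroup against 2 overall. These figures are by findings at entry; carrying them over to follow-up findings is an assumption.

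At stake is the estimated benefit of successive exams. It feeds question 6b (at least one, or two or more exams) and question 6d (when risk is low enough to stop). More follow-up or more cancers would make the estimate more precise but would not remove the bias.

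**Working it through.** The plan gives no figure for this bias, so there is none to reproduce. The question is how large it could be under inputs the documents make plausible.

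**Inputs from the documents**
- Prevalence *q* of advanced findings at follow-up: about 3% by 3 years (section 2.2.2); 5.2% and 8.6% at two and four years in one randomised trial (section 2.2.3); 3% and 5% intermediate- or high-risk lesions in section 2.8; and 198/6,600 = 3% in the sample size table. Range used: 3% to 8.6%.
- Second follow-up among those with a first, intermediate-risk hospital cohort (Appendix 1.0): 3,773/7,046 = 53.5%.

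**Assumed inputs**
- True HR of the further visit 0.60.
- Attendance *a* = 80% after an advanced finding and *b* = 40% otherwise.
- CRC hazard multiplied by *R* = 2 or 3 after an advanced finding. The ratio 4.5/2 = 2.25 from section 2.8 lies between.

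**Formula.** The share with advanced findings is p1 = qa/[qa + (1−q)b] among attenders and p0 = q(1−a)/[q(1−a) + (1−q)(1−b)] among non-attenders. Then

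observed HR = true HR × [1 + p1(R−1)] / [1 + p0(R−1)].

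| q | p1 | p0 | R = 3 | R = 2 |
|---|---|---|---|---|
| 3% | 0.024/0.412 = 0.058 | 0.006/0.588 = 0.010 | 0.60 × 1.1165/1.0204 = 0.66 | 0.60 × 1.0583/1.0102 = 0.63 |
| 5% | 0.040/0.420 = 0.095 | 0.010/0.580 = 0.017 | 0.60 × 1.1905/1.0345 = 0.69 | 0.60 × 1.0952/1.0172 = 0.65 |
| 8.6% | 0.0688/0.4344 = 0.158 | 0.0172/0.5656 = 0.030 | 0.60 × 1.3168/1.0608 = 0.74 | 0.60 × 1.1584/1.0304 = 0.67 |

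**Cross-check on attendance.** The 80%/40% split implies 41% to 43% overall attendance, below the observed 53.5%. Overall attendance was therefore fixed at 53.5%, with an attendance odds ratio of 2 to 4, 5% to 10% positive findings and R from 2.25 to 5. The HR is then multiplied by 1.04 to 1.37, which takes 0.60 to between 0.62 and 0.82. With an odds ratio of 1 the factor is 1.00: without findings-driven attendance this bias disappears.

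**Would adding findings to the same model suffice?** In simulated cohorts of 40,000 (one run per scenario, about 30% positive findings, true HR 0.70 for each exam), findings were entered as a time-updated covariate in the model from baseline. The second-exam HR was then 0.69 to 0.76 at an attendance odds ratio of 4, and 0.71 to 0.85 at an odds ratio of 2, with sampling error. But the first-exam HR moved from about 0.60–0.78 to about 0.30–0.57, against a true 0.70. Findings exist only after the first exam, so its coefficient becomes a contrast between people with a clear exam and everyone not yet examined. In practice, findings at later visits are also affected by earlier surveillance.

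**The case against.** Several points on the other side stand.

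- **Baseline only is a reading.** The adjustment sentence does not say when the characteristics are measured, and section 2.9.3 mentions findings at the last examination for its descriptive step. The adjacent sentence and section 2.3.1 still support the reading, and nothing puts follow-up findings in the Cox model.
- **The stopping suggestion needs two negative exams.** A patient with one negative follow-up may still be due a second, so the rule acts mainly on third and later visits. No passage shows that attendance at the second visit depends on first follow-up findings; 80% versus 40% is an assumption.
- **A reader might infer that the bias could hide most of the benefit.** With 25% advanced findings and a 3-fold hazard, the formula gives 0.60 × 1.8/1.2 = 0.90. The documents do not support that prevalence. The 30% to 50% recurrence in section 2.2.1 is for any adenoma, and section 2.2.1 describes new adenomas at follow-up as mostly diminutive.
- **A reader might infer that questions 6b and 6d rest on this coefficient, or that stopping would look falsely safe.** Both also use Kaplan-Meier risk and comparison with the general population. On an absolute-risk criterion, enriching later-visit groups with higher-risk patients makes stopping look less safe. Neither inference is established.
- **A reader might infer that symptom-prompted colonoscopies count as exposure.** Section 2.9.3 speaks of surveillance visits when discussing intervals, and the hospital records are matched to identify surveillance colonoscopies. The covariate's wording needs one clarifying line, no more.

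**Conclusion.** The point holds in limited form, as something the plan should fix. A decision-relevant HR has no stated control for findings that can drive both further visits and CRC. Under the illustrated assumptions, a true 0.60 would appear as about 0.66 to 0.74 with a 3-fold hazard, or 0.63 to 0.67 with a 2-fold hazard. The benefit would be understated but still visible; a larger bias in that illustration needs a higher prevalence of advanced findings than the plan cites. These figures assume that the findings are not already captured by the baseline covariates and that no other selection operates. Because selection on age or frailty could act the other way, neither the net size nor the net direction can be fixed from the documents.

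**What to change.** Keep the baseline-adjusted Cox model and report beside it an analysis of second and later exams that handles earlier findings. Either of these would do:

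1. A Cox model starting at first follow-up, adjusted for baseline and first follow-up findings, and extended visit by visit where events allow. This is the simpler option.
2. A marginal structural Cox model with stabilised, truncated weights for attending each next visit, given baseline covariates, findings at all previous visits, age and time since last exam.

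Do not simply add time-updated findings to the model from baseline.

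State that the visit covariate counts surveillance examinations, identified by recorded indication, and treat symptom-prompted colonoscopies separately. The hospital databases are described as recording "indication for colonoscopy and diagnosis, and the size and location of any polyps detected", so no new collection is evident.

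The cost is SAP wording and extra modelling. The downsides are wider confidence intervals and possibly unstable weights: section 2.8 reports about 50 CRCs in the smallest risk group at 6 years of follow-up. Check positivity, report the weight distribution, and pool risk groups if needed.
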